**APPENDIX 5. LIST OF ADVERSE EVENTS OF SPECIAL INTEREST**

Adverse Event Terms per Protocol	Associated MedDRA Preferred Terms
Creatine kinase elevations	Blood creatine phosphokinase abnormal
Creatine kinase elevations	Blood creatine phosphokinase increased
Creatine kinase elevations	Blood creatine phosphokinase MM abnormal
Creatine kinase elevations	Blood creatine phosphokinase MM increased
New onset or worsening diabetes mellitus	Blood glucose abnormal
New onset or worsening diabetes mellitus	Blood glucose increased
New onset or worsening diabetes mellitus	Diabetes mellitus
New onset or worsening diabetes mellitus	Diabetes mellitus inadequate control
New onset or worsening diabetes mellitus	Diabetic ketoacidosis
New onset or worsening diabetes mellitus	Glucose tolerance impaired
New onset or worsening diabetes mellitus	Glucose urine present
New onset or worsening diabetes mellitus	Glycosuria
New onset or worsening diabetes mellitus	Glycosylated haemoglobin increased
New onset or worsening diabetes mellitus	Hyperglycaemia
New onset or worsening diabetes mellitus	Impaired fasting glucose
New onset or worsening diabetes mellitus	Ketoacidosis
New onset or worsening diabetes mellitus	Ketosuria
New onset or worsening diabetes mellitus	Ketosis
New onset or worsening diabetes mellitus	Type 2 diabetes mellitus
New onset or worsening diabetes mellitus	Urine ketone body present
Hepatic disorders	Alanine aminotransferase abnormal
Hepatic disorders	Alanine aminotransferase increased
Hepatic disorders	Aspartate aminotransferase abnormal
Hepatic disorders	Aspartate aminotransferase abnormal
Hepatic disorders	Blood bilirubin abnormal
Hepatic disorders	Blood bilirubin increased
Hepatic disorders	Hepatic enzyme abnormal
Hepatic disorders	Hepatic enzyme increased

Version Number: 1.7  
 Version Date: 21Mar2018

Adverse Event Terms per Protocol	Associated MedDRA Preferred Terms
Hepatic disorders	Hypertransaminasaemia
Hepatic disorders	Liver function test abnormal
Hepatic disorders	Liver function test increased
Hepatic disorders	Transaminases abnormal
Hepatic disorders	Transaminases increased
Hypoglycemia	Blood glucose abnormal
Hypoglycemia	Blood glucose decreased
Hypoglycemia	Hypoglycaemia
Hypoglycemia	Hypoglycaemic coma
Hypoglycemia	Hypoglycaemic encephalopathy
Hypoglycemia	Hypoglycaemic seizure
Hypoglycemia	Shock hypoglycaemic
Metabolic acidosis	Metabolic acidosis
Muscular disorders	Muscular weakness
Muscular disorders	Muscle necrosis
Muscular disorders	Muscle spasms
Muscular disorders	Myalgia
Muscular disorders	Myoglobin blood increased
Muscular disorders	Myoglobin blood present
Muscular disorders	Myoglobin urine present
Muscular disorders	Myoglobinaemia
Muscular disorders	Myoglinuria
Muscular disorders	Myopathy
Muscular disorders	Myopathy toxic
Muscular disorders	Necrotizing myositis
Muscular disorders	Pain in extremity
Muscular disorders	Rhabdomyolysis
Neurocognitive/Neurologic disorders	Amnesia
Neurocognitive/Neurologic disorders	Cognitive disorder
Neurocognitive/Neurologic disorders	Confusional state
Neurocognitive/Neurologic disorders	Disorientation
Neurocognitive/Neurologic disorders	Memory impairment
Neurocognitive/Neurologic disorders	Mental status changes
Renal disorders	Acute kidney injury
Renal disorders	Acute prerenal failure
Renal disorders	Blood creatinine abnormal

[Redacted]

Version Number: 1.7  
 Version Date: 21Mar2018

[Redacted]

Adverse Event Terms per Protocol	Associated MedDRA Preferred Terms
Renal disorders	Blood creatinine increased
Renal disorders	Blood urea abnormal
Renal disorders	Blood urea increased
Renal disorders	Blood urea nitrogen/Creatinine ratio increased
Renal disorders	Creatinine renal clearance abnormal
Renal disorders	Creatinine renal clearance decreased
Renal disorders	Glomerular filtration rate abnormal
Renal disorders	Glomerular filtration rate decreased
Renal disorders	Gout
Renal disorders	Oliguria
Renal disorders	Prerenal failure
Renal disorders	Renal failure
Renal disorders	Renal function test abnormal
Renal disorders	Renal impairment

[Redacted]

Version Number: 1.7  
 Version Date: 21Mar2018

[Redacted]

Addendum to Statistical Analysis Plan

---

**Title:** A RANDOMIZED, DOUBLE-BLIND, PARALLEL GROUP, MULTICENTER STUDY TO EVALUATE THE EFFICACY AND SAFETY OF BEMPEDOIC ACID (ETC-1002) 180 MG COMPARED TO PLACEBO ADDED TO BACKGROUND LIPID-MODIFYING THERAPY IN PATIENTS WITH ELEVATED LDL-C WHO ARE STATIN INTOLERANT

**Protocol:** ETC-1002-046

**Clinical Phase:** 3

**Product:** ETC-1002

**Date:** Dec 18, 2018

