#### 19.1.1. ALL TEAEs

Incidence of TEAEs will be presented by System Organ Class (SOC) and Preferred Term (PT) and also broken down further by maximum severity and relationship to study medication. Adverse events by the subgroups in [Section 18.2.4](#) with the exception of baseline LDL subgroup will also be presented.

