**19.1.4. ADVERSE EVENTS OF SPECIAL INTEREST (AESI)**

Adverse events of special interest will be identified by pre-specified MedDRA preferred terms provided by Esperion Therapeutics Inc. (see [Appendix 5](#)). These events will be summarized by AESI category, SOC and PT. All AESI will be summarized by severity and relationship to study medication. In addition, AESI will be evaluated by monitoring safety labs as detailed in [section 19.4](#).

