### 19.4. LABORATORY EVALUATIONS

Results from the central laboratory will be included in the reporting of this study for Hematology, Blood Chemistry, Lipids, Coagulation, HbA1c, hsCRP and Urinalysis. A list of laboratory assessments to be included in the outputs is included in Protocol, [Section 10.1.6.1](#).

Presentations will use SI Units and conventional units.

Quantitative laboratory measurements reported as “< X”, i.e. below the lower limit of quantification (BLQ), or “> X”, i.e. above the upper limit of quantification (ULQ), will be converted to X for the purpose of quantitative summaries, but will be presented as recorded, i.e. as “< X” or “> X” in the listings.

The formula to calculate eGFR is:  $eGFR = 186 \times (\text{Creatinine} / 88.4)^{-1.154} \times (\text{Age})^{-0.203} \times (0.742 \text{ if female}) \times (1.210 \text{ if black})$ , where creatinine is in mmol/L.

Summaries for all lab results, including unscheduled visit values, will be included for below analyses:

- Observed and change/percent change from baseline by visit (for quantitative measurements).

[REDACTED]

Version Number: 1.7  
 Version Date: 21Mar2018

[REDACTED]

- Observed and change/percent change from baseline for HbA1c and glucose by history of diabetes and visit.
- Shift from baseline by visit according to normal ranges.
- Shift from baseline according to normal ranges for HbA1c and glucose by history of diabetes and visit.
- eGFR and values of CK will be summarized by treatment group and by baseline eGFR categories (low, normal, high).
- Potential Hy’s law cases (>3 × ULN for ALT and/or AST with concurrent Total Bilirubin >2 × ULN) will be tabulated listed.
- Laboratory abnormalities in parameters of interest

ALT or AST (> 3x ULN , >5xULN)

TB (>2x ULN)

CK (> 5x ULN) and (>10x ULN)

Fasting Blood Glucose (≤50 mg/dL, ≥126 mg/dL) by history of diabetes

HbA1c (≥6.5%) by history of diabetes

Creatinine (change from baseline for >1 mg/dL )

eGFR (< 15 mL/min/1.73m^2, 15 –< 30 mL/min/1.73m^2)

Hgb (decrease from baseline for ≥2 g/dL)

Hgb (<8 g/dL)

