### APPENDIX 3. LIST OF DMC TABLES, LISTINGS AND FIGURES

#### TABLES

- 14.1.1.1 Patient Disposition – All Patients
- 14.1.2.1a Demographic and Other Baseline Characteristics – Full Analysis Set
- 14.1.3.1 Medical/Surgical History – Full Analysis Set
- 14.1.3.3 Targeted Cardiovascular History/Risk Factors – Full Analysis Set
- 14.1.5.1 Study Drug Compliance – Safety Analysis Set
- 14.3.1.1 Overview of Treatment-Emergent Adverse Events – Safety Analysis Set
- 14.3.1.2 Treatment-Emergent Adverse Events by Maximum Severity, System Organ Class and Preferred Term – Safety Analysis Set
- 14.3.1.3 Serious Treatment-Emergent Adverse Events by Maximum Severity, System Organ Class and Preferred Term – Safety Analysis Set
- 14.3.1.4 Related Treatment-Emergent Adverse Events by Maximum Severity, System Organ Class and Preferred Term – Safety Analysis Set
- 14.3.1.5 Related Serious Treatment-Emergent Adverse Events by Maximum Severity, System Organ Class and Preferred Term – Safety Analysis Set
- 14.3.1.6 Treatment-Emergent Adverse Events That Led to Discontinuation of Study Drug by Maximum Severity, System Organ Class and Preferred Term – Safety Analysis Set
- 14.3.1.8 Treatment-Emergent AESIs by Maximum Severity, System Organ Class and Preferred Term – Safety Analysis Set
- 14.3.1.15 Investigator-reported Major Cardiac Events (MACE) by Event Type – Safety Analysis Set
- 14.3.1.16 Adjudicated Major Cardiac Events (MACE) by Event Type – Safety Analysis Set
- 14.3.2.8 Laboratory Parameters of Interest: Observed and Change from Baseline – Safety Analysis Set
- 14.3.2.9 Laboratory Parameters of Interest: Laboratory Abnormalities – Safety Analysis Set

Version Number: 1.7  
 Version Date: 21Mar2018

14.3.2.10 Quantitative Clinical Laboratory Evaluations: Lipids – Safety Analysis Set (note that this table is produced for DMC only)

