## Addendum to the Statistical Analysis Plan for Study 1002-046

### Post-hoc Analyses

Esperion completed the planned analysis as described in Study 1002-046 SAP for all data collected in the study.

After unblinding, some issues of clinical interest were identified. To address these issues, post-hoc analyses were performed to summarize the following: statin related adverse events prior to study entry, patients experiencing repeated and confirmed abnormal liver function tests after randomization, and percent change from baseline in LDL-C over time by background lipid modifying therapy (LMT). Finally, a sensitivity analysis was performed for the primary endpoint with Site 1020 excluded, since this was closed prematurely based on administrative and site accessibility issues.

The listing of tables for the post-hoc analyses is provided in the table below.

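### The hepatic AESI term list in SAP Appendix 5 prints the AST 'abnormal' term twice and omits its 'increased' partner, so AST-increase events would drop out of the hepatic AESI tables if the list is applied as printed

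*SAP*

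**What the plan says.** SAP 19.1.4 makes the term list the selection rule: "Adverse events of special interest will be identified by pre-specified MedDRA preferred terms", with Appendix 5 as the reference. The selected events are summarized by AESI category, system organ class and preferred term, and also by severity and relationship to study medication. The section adds a second route: "In addition, AESI will be evaluated by monitoring safety labs", with details in SAP 19.4.

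Under hepatic disorders, Appendix 5 prints "Aspartate aminotransferase abnormal" on two consecutive rows. No other AST term appears in the appendix.

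SAP Appendix 3 lists the tables sent to the DMC. They include Table 14.3.1.8, "Treatment-Emergent AESIs by Maximum Severity, System Organ Class and Preferred Term", and Table 14.3.2.9, "Laboratory Parameters of Interest: Laboratory Abnormalities".

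The SAP addendum of December 2018 states that the sponsor "completed the planned analysis as described in Study 1002-046 SAP for all data collected in the study". It adds a post-hoc summary of post-randomization abnormal liver function (Table 17.5.1.1) but does not amend Appendix 5.

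**The concern.** A repeated row adds nothing to a lookup, so the second AST row has no function as printed. The term one would expect in its place, aspartate aminotransferase increased, is absent. Other listed hepatic terms, such as those for transaminases or hepatic enzymes increased, are separate preferred terms and would not capture an event coded to AST increased.

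The hepatic AESI total, and its breakdown by preferred term, severity and relationship, could therefore be under-counted, both in the final tables and in the DMC's AESI table.

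AST matters in this programme. Protocol 10.2.11.1 reports 7 patients on bempedoic acid with repeated and confirmed ALT and/or AST above 3 times ULN in earlier studies. Protocol 10.2.11.3.2 sets follow-up triggered by ALT or AST. The addendum names repeated and confirmed abnormal liver function tests among the issues identified after unblinding.

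**Working it through.** The plan gives no figure to reproduce. The check is a count of Appendix 5 and a trace of where the list is used.

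**Row count, by AESI category**

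| Category | Rows | Distinct terms |
|---|---|---|
| Creatine kinase elevations | 4 | 4 |
| New onset or worsening diabetes | 16 | 16 |
| Hepatic disorders | 13 | 12 |
| Hypoglycemia | 7 | 7 |
| Metabolic acidosis | 1 | 1 |
| Muscular disorders | 14 | 14 |
| Neurocognitive/neurologic | 6 | 6 |
| Renal disorders | 17 | 17 |
| **Total** | **78** | **77** |

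78 − 77 = 1, so there is exactly one repeat within a category: the AST row. The blood glucose 'abnormal' term also occurs twice, but under two different categories (diabetes and hypoglycemia), so it is not a repeat of this kind.

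**Pairing within the hepatic block**

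| Concept | 'Abnormal' listed | 'Increased' listed |
|---|---|---|
| ALT | yes | yes |
| AST | yes, twice | **no** |
| Blood bilirubin | yes | yes |
| Hepatic enzyme | yes | yes |
| Liver function test | yes | yes |
| Transaminases | yes | yes |

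Five of six pairs are complete. These six concepts take 6 × 2 = 12 rows, and hypertransaminasaemia makes 13. With the second AST row corrected, the block would have 13 distinct terms in 13 rows and six complete pairs. Outside the hepatic block, 8 of 9 'abnormal' terms have an 'increased' or 'decreased' partner. The exception, the renal function test term, is not duplicated.

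**Effect if the list is applied as printed**

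- *Preferred-term level:* every event coded to AST increased is absent from the hepatic AESI tables.
- *Patient level:* let A be the patients with an AST-increased event and B the patients with at least one of the 12 listed hepatic terms. The category count is |B| where it should be |A ∪ B|. The shortfall is |A \\ B|, the patients with AST increased and no other listed hepatic term. A patient who also has ALT increased, for example, is still counted. The documents give no event data, so the shortfall cannot be computed.

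**Where AST remains visible**

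- SAP 19.1.1: all treatment-emergent events by system organ class and preferred term. The DMC also receives such a table (14.3.1.2).
- SAP 19.4: ALT or AST above 3 and above 5 times ULN, shifts by normal range, and potential Hy's law cases. The DMC receives laboratory abnormalities in Table 14.3.2.9.
- Addendum: Table 17.5.1.1.

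**The case against.** The strongest case on the other side is that this is an erratum with little consequence. The planned hepatic safety analysis in Protocol 11.7 rests on laboratory values and Hy's law criteria, and hepatic monitoring is triggered by laboratory thresholds. Under Protocol 10.1.6.4, an abnormal value not already associated with an adverse event becomes one only if it leads to action on study drug, needs intervention or is judged clinically significant. Adverse event terms are thus a selective, secondary view of AST, and SAP 19.1.4 plans no test on them. The terms were supplied by the sponsor, so Appendix 5 may be only a printed copy of a correct file. The missing term is inferred, because the MedDRA dictionary is not in the documents. The text was also read from PDF by a program.

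Much of this stands. It is why the point is minor, why the effect is stated only for the list as printed, and why the intended term should be confirmed before the row is changed. Three parts do not remove the point:

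- A PDF-reading fault is unlikely, since both rows are intact and sit in an otherwise regular sequence. A glance at the source page settles it.
- The laboratory threshold table does not replace the AESI count. No multiple of ULN is required for an AST rise to be reported as an adverse event, so an AST event at or below 3 times ULN would not appear in that table.
- Appendix 5 is the only selection rule that the SAP states. A correct file elsewhere would still leave the SAP wrong as written.

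**Conclusion.** The concern holds. Appendix 5 repeats one AST term and omits the other, and neither SAP version 1.7 nor its addendum corrects this. Followed as written, the list under-selects hepatic AESIs.

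The severity is minor. One term of an intended 13 is missing from one descriptive category. No endpoint or hypothesis test is touched, and AST remains visible in the general adverse event and laboratory tables.

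The conclusion rests on two assumptions: that the intended term is AST increased, which the pairing strongly supports, and, for any effect on results, that the programmed lookup follows the printed list. The documents cannot confirm the second.

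**What to change.** 1. Confirm the intended term against the source page and MedDRA version 20.1 (the version named in SAP 19.1), then replace the second AST row of Appendix 5 with the 'increased' term.
2. Check whether the programmed AESI lookup has the duplicate or the correct term.
3. If the lookup was correct, a one-line erratum to Appendix 5 is enough.
4. If it carried the error, rerun the final hepatic AESI tables and record the change in the study report as a post-unblinding correction, since the addendum describes the planned analysis as complete. In my judgement, past DMC tables need not be rerun, because the DMC also had the preferred-term and laboratory tables.

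The cost is one row and one lookup check and, at worst, a rerun of a few tables with a note. The hepatic patient count can only stay the same or rise, so the correction cannot hide a liver signal. If the duplicate row had caused matched records to be counted twice, event counts for the AST 'abnormal' term could fall; the lookup check should cover that as well.

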## Addendum to the Statistical Analysis Plan for Study 1002-046

### Post-hoc Analyses

Esperion completed the planned analysis as described in Study 1002-046 SAP for all data collected in the study.

After unblinding, some issues of clinical interest were identified. To address these issues, post-hoc analyses were performed to summarize the following: statin related adverse events prior to study entry, patients experiencing repeated and confirmed abnormal liver function tests after randomization, and percent change from baseline in LDL-C over time by background lipid modifying therapy (LMT). Finally, a sensitivity analysis was performed for the primary endpoint with Site 1020 excluded, since this was closed prematurely based on administrative and site accessibility issues.

The listing of tables for the post-hoc analyses is provided in the table below.

#### **Listing of new Tables for Study 1002-046.**

Table 17.1.1.1	Statin Related Adverse Effect/ Full Analysis Set
Table 17.2.1.1	Primary Efficacy Post-hoc Analysis: Percent Change from Baseline in Low Density Lipoprotein Cholesterol (LDL-C)/ Excluding Site 1021/ Full Analysis Set
Table 17.3.1.1	Primary Efficacy Post-hoc Analysis: Percent Change from Baseline in Low Density Lipoprotein Cholesterol (LDL-C)/ By Background Lipid Modifying Therapy Lipid Modifying Treatment Subgroup/ Observed Data/ Full Analysis Set
Table 17.4.1.1	Primary Efficacy Post-hoc Analysis: Percent Change from Baseline in Low Density Lipoprotein Cholesterol (LDL-C)/ By Background Lipid Modifying Therapy Lipid Modifying Treatment Subgroup/ On-Treatment Analysis/ Full Analysis Set
Table 17.5.1.1	Post-Randomization Abnormal Liver Function Summary/ Safety Analysis Set
